We will prospectively recruit 60 patients with NP derived from different etiologies (study #1: PASC, study #2: CIPN). Randomization will be done through a computer-generated list followed by sequential allocation.

Patients will be followed-up and monitored for up to 8 weeks. The study will be double-blinded (clinicians and patients) until the 4th week, where study participants will be told of their group assignment.

The following characteristics will be included: 1. Frequency: 3+ hours daily. 2. Patient reported outcomes: Fibromyalgia Diagnostic Criteria (FMS), Symptom Impact Questionnaire (SIQR), Patients Global Impression of Change (PGIC), Brief pain inventory (BPI), Medical Outcome Study Sleep Scale (MOS) questionnaires, and Multidimensional Assessment of Fatigue (MAF), common terminology criteria for adverse events (CTCAE) v5., EORTC-CIPN20, UENS, EORTC-QLQC30 3. Perfusion test: Lower limb calf tissue oxygen saturation (Kent Imaging System) 4. Other measurements: pulse oximetry, muscle calf activation in response to TENS (surface electromyography [sEMG] assessment), muscle calf activation in response to ankle maximum voluntary contraction (sEMG assessment), ankle strength (measured using ankle dynamometer), peripheral neuropathy (DPNCheck), vibration perception threshold (VPT test). 5. Time points: The outcome measures will be obtained at baseline and four weeks. 6. Optional questionnaires collected at each time point: instrumental activity of daily living scale (IADL), daily living independence (KATZ), depression (CES-D), fatigue (FACT), cognitive assessment (MOCA), pain and mobility, global health (PROMIS), sleep (PSQI), frailty (TSFI), anxiety (BAI), and user acceptability (TAM). 7. Optional assessments of the 6-minute walk test, gait speed, balance, frailty and physical monitoring will be conducted at both study visits using wearable sensors. 8. Optional: Patients keep the device after the study ends

(those who wore sham will get an active device).

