The cohorts (per sub-study) will be randomized in two arms: Active group (AG). The AG (n=15) will be undergoing TENS therapy with an active device during 4 weeks. To deliver TENS, a band strap with hydrogel pads will be placed around the calf muscle of one lower-extremity alternating to the other side in a weekly basis. We hypothesize that a high dose nerve stimulation has a widespread effect on pain and other symptoms, not just at the location of stimulation. To get localized effects in both limbs the subjects will alternate limbs. We also recommend this in any case to minimize the risk of skin irritation from the hydrogel pads. According to previous studies, perceived afferent stimulation by the brain from only one limb is able to send efferent signals to both limbs. Therefore, both limbs will be assessed for therapy outcomes.

Placebo Group (PG). The PG (n=15) will be undergoing TENS therapy with a sham device as described in the AG. The sham device is identical to the active device in all respects except that it stimulates for 6 minutes during each therapy session instead of 60 minutes, and is therefore 10% of the dose.

Both groups will receive their respective devices at the initial visit (BL) and will be asked to return in 4 weeks for follow-up assessment (4W visit). At this 4 week visit, study participants will be unblinded and the active group will keep their active device, while the placebo group will receive a placebo device. Study participants will return for a final in-person visit at the 8th week (8W), which will include the assessments described above. Throughout this 8-week period the participants may receive follow-up phone calls assessing their compliance. All subjects will keep their active device after completion of the 8-week study.

Inclusion Criteria:

Study #1: Previous COVID-19 infection Persistent symptoms for lower extremity pain, fatigue, weakness, or poor gait and balance after infection assessed by critical care clinicians on the initial consultation Willing to attend clinic for assessments

Study #2: Patients with chemotherapy induced peripheral neuropathy in current active or having finished treatment for any type of cancer that requires chemotherapy regardless of dosage. Willing to attend clinic for assessments

Exclusion Criteria:

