Study #1: Severe cognitive decline reduces their ability to interact with the TENS mobile app Major visual or hearing weakness reduces the ability to interact with TENS mobile app Unable to walk independently for a distance of 10 meter Major foot problems such as active lower extremity wounds, major foot deformity (e.g., Charcot Foot), previous major amputations, and claudication Demand-type cardiac pacemaker, implanted defibrillator, or other implanted electronic devices; and any conditions that may interfere with outcomes or increase the risk of the use TENS based on the judgement of clinicians

Study #2: Severe cognitive decline reduces their ability to interact with the TENS mobile app Major visual or hearing weakness reduces the ability to interact with TENS mobile app Unable to walk independently for a distance of 10 meter Major foot problems such as active lower extremity wounds, major foot deformity (e.g., Charcot Foot), previous major amputations, and claudication Demand-type cardiac pacemaker, implanted defibrillator, or other implanted electronic devices; and any conditions that may interfere with outcomes or increase the risk of the use TENS based on the judgement of clinicians. Patients with metastatic or terminal cancer disease.

F2. Procedure

30 subjects per sub-study (study #1: 30 subjects, study#2: 30 subjects):

Aim 1 (acceptability): To examine feasibility and acceptability of TENS in patients with NP.

At the baseline visit and each of the follow-up visits (at four weeks, 4W; and eight weeks, 8W), electrical stimulation using the TENS device, will be administered by the coordinator. Daily electrical stimulation, between the baseline and follow-up visit, will be administered by the patient at their convenience. They will be asked to use the device at least 3 hours per day for at least 4 days per week. At follow-up study visits (4W and 8W), a Technology Acceptance Model (TAM) survey adopted for tele-health and smart wearables applications perception of benefit, technological anxiety, technology acceptance, trust, facilitation conditions, risk, and attitude of use will be obtained for each subject.

Aim 2 (proof of concept effectiveness): To examine effectiveness of TENS for NP.

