At the baseline visit (BL) and each of the follow-up visits (at four weeks, 4W; and eight weeks, 8W), electrical stimulation using the TENS device, will be administered by the coordinator. This trial will have 30 patients divided into two groups. Group 1 (Active group, n=15) will receive a functional Neurometrix Quell Relief Device; Group 2 (Placebo group, n=15) will receive a non-functional Neurometrix Quell Relief Device that will administer 6 minutes of stimulation per hour of stimulation. Lower extremity muscle activation will be assessed by using sEMG (electromyography) at each study visit during the delivery of stimulation. At the 4th week (4W), both groups will be unblinded and the AG will keep their functional device, will the PG will return their non-functional device and receive a functional device. The patients will be monitored for another 4 weeks with a final follow-up visit at 8 weeks (8W). Both the AG and PG will have the option to take home their functional device at the end of the 8-week study

Tissue Oxygen Saturation: near infrared imaging (Kent Imaging System) at pre-, 30min, 60min, and 30min post-treatment (after stopping of EE device) at each study visit.

Patient reported outcomes: Fibromyalgia Diagnostic Criteria (FMS), Symptom Impact Questionnaire (SIQR), Patients Global Impression of Change (PGIC), Brief pain inventory (BPI), Medical Outcome Study Sleep Scale (MOS) questionnaires, and Multidimensional Assessment of Fatigue (MAF), Common Terminology Criteria for Adverse Events (CTCAE) v5., European Organization for Research and Treatment of Cancer Quality of Life Questionnaire-CIPN twenty-item scale (EORTC-CIPN20), Utah Early Neuropathy Scale (UENS), European Organization for Research and Treatment Core Quality of Life questionnaire (EORTC-QLQC30).

Peripheral Neuropathy: Peripheral neuropathy will be assessed at BL, 4W, and 8W using DPNCheck (Neurometrix, Woburn, MA, USA). This is a noninvasive device which will measure conduction velocity and amplitude. Vibration perception threshold (VPT) will also be used to assess sensitivity of patients' lower extremity.

Optional assessments: Oxygen Level Assessment: Oxygen saturation will be measured using a pulse oximeter.

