This study brings no more than minimal risk to subjects as it only involves a non-invasive device. There are some risks associated with lack of comfort from TENS, skin allergy to the TENS band, risk associated with electrical mal-function of the TENS device, and other unknown risks. All TENS devices will be checked before any use to minimize the risk associated with electrical malfunction. All TENS devices are FDA approved for the purpose of temporary relief of pain. However, these devices have not been used before for purpose of managing COVID-19 side effects like the purpose of this study. Although there is no direct benefit for participating in the study, their participation may help the investigators design a practical assessing method to identify the impact of COVID-19. The peripheral neuropathy device (DPNCheck) has minimal risks to the subjects as it is non-invasive, safe, non-toxic, and non-ionizing. The subjects may feel a tingling sensation during its use, and if it is too intense, the research staff will stop the test.

Study #2:

The risk to participants of this study is considered to be minimal because all that is required is simple walking in a controlled environment with a research staff present (all subjects will be mobile, and walking as a regular part of their activities of daily living this research routine will not place them at higher risk than normal activities of daily living). No more risk of harm or discomfort is associated with these tests than the discomfort normally incurred while walking or during normal muscle stretching. The peripheral neuropathy device (DPNCheck) has minimal risks to the subjects as it is non-invasive, safe, non-toxic, and non-ionizing. The subjects may feel a tingling sensation during its use, and if it is too intense, the research staff will stop the test.

Section J: Consent Procedures

J1. Waiver of Consent

Will any portion of this research require a waiver of consent and authorization?

No

J1a. Waiver of requirement for written documentation of Consent

Will this research require a waiver of the requirement for written documentation of informed consent?

No

J2. Consent Procedures

Who will recruit subjects for this study?

PI
PI's staff

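### Neither sub-study excludes previous Quell users or participants in the other sub-study, although session length is the only thing that separates sham from active

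*Combined protocol and SAP*

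**What the plan says.** **Sham and blinding.** F1 (Placebo Group) describes the sham as "identical to the active device in all respects except that it stimulates for 6 minutes during each therapy session instead of 60 minutes". It puts the sham's share of the active dose at 10%. F2 (Aim 2) calls it a "non-functional Neurometrix Quell Relief Device that will administer 6 minutes of stimulation per hour of stimulation". On blinding, F1 states: "The study will be double-blinded (clinicians and patients) until the 4th week".

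**Eligibility.** The inclusion criteria in F1 ask for persistent symptoms after COVID-19 (Study #1) or chemotherapy-induced neuropathy (Study #2), plus willingness to attend. Neither asks that patients be new to TENS. The exclusion lists cover cognition, vision and hearing, walking 10 metres, foot problems, and then "Demand-type cardiac pacemaker, implanted defibrillator, or other implanted electronic devices; and any conditions that may interfere with outcomes or increase the risk". That clause goes on to leave the decision to clinicians' judgement. Study #2 alone adds metastatic or terminal cancer. Neither list mentions previous Quell use, other TENS use or the other sub-study.

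**Devices after the study.** F1 says: "All subjects will keep their active device after completion of the 8-week study". Elsewhere in F1, and in F2, keeping it is described as optional.

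**Outcomes and analysis.** Section D names pain symptoms, sleep and fatigue as primary. G2 tests the intervention effect with mixed models or GEE, and allows adjustment for baseline differences and other prognostic variables.

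**The concern.** The arms are meant to differ in one respect that a patient can perceive: whether stimulation stops after 6 minutes or continues for 60. A patient who has used a Quell device before, or has completed the other sub-study, brings the reference needed to tell them apart. The criteria as written admit that patient.

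All participants are unblinded at week 4, so the first four weeks are the only sham-controlled evidence. The instruments listed for pain, sleep and fatigue (BPI, MOS sleep scale, MAF) are questionnaires, so what patients believe about their device can affect the result directly. A sham patient who recognises the sham would be expected to report less improvement. An active patient who recognises a full session might report more. Both would favour TENS.

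**Working it through.** **1. The plan's own figure.** 6 / 60 = 0.10, which agrees with the stated 10% dose. Arms of 15 + 15 = 30 per sub-study and 2 × 30 = 60 also agree with the plan.

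**2. How often a patient meets the cue.** Section D gives 3 to 5 hours of stimulation a day. At 60 minutes per session:
- sham: 3 × 6 = 18 to 5 × 6 = 30 minutes a day
- active: 3 × 60 = 180 to 5 × 60 = 300 minutes a day

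F2 asks for at least 3 hours a day on at least 4 days a week. Over the blinded period that is 3 × 4 × 4 = 48 sessions or more, self-administered at home. An experienced user would have many occasions to notice.

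**3. Whether anything in the eligibility text closes the gap.**

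| Route | Text that could bar it | Does it? |
|---|---|---|
| Previous Quell user | Clinician-judgement clause | Only if a clinician asks and treats past use as an interfering condition |
| Participant in the other sub-study | Target of 60 patients (F1) | Implies separate people but sets no rule |
| User of another TENS unit | Same clause | As for the first row |

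**4. Whether such patients are plausible.** The background section says Quell has been employed in fibromyalgia, CIPN and PASC, among other conditions. Section I (Study #1) says: "All TENS devices are FDA approved for the purpose of temporary relief of pain". It adds that the devices had not been used before for COVID-19 effects. That sits awkwardly with the background section, and the two should be reconciled. Neither statement gives a rate of use among the clinics' patients.

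**5. Chance of at least one experienced user in a sham arm.** The share p of enrolees with such experience is an assumption. The formula is 1 − (1 − p)^15:
- p = 5%: 1 − 0.95^15 = 54%
- p = 10%: 1 − 0.90^15 = 79%
- p = 20%: 1 − 0.80^15 = 96%

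Nothing in the documents shows that the share of previous Quell users reaches even 5%. One such patient is 1/15 = 6.7% of the arm.

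No effect in points is derived, because the documents supply neither the number of experienced users nor the effect of recognition on a score.

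**The case against.** **The clinician clause already covers this.** In part. It lets a clinician turn away someone whose condition may interfere with outcomes. It names neither device experience nor dual participation, and nothing prompts the question, so it is not a uniform rule.

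**Any TENS owner could unmask the sham.** A reader might infer this, but the documents do not support it. Owning another make of unit does not teach someone that a Quell session lasts 60 minutes. Recognition applies mainly to previous Quell users. The documents reviewed also do not show what participants are told about session length, or what the app displays.

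**Patients new to TENS may notice too.** This stands. Stimulation that stops after 6 minutes can be felt by anyone, and no check of blinding is described. Exclusion deals only with the patients best placed to recognise the sham.

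**Dual enrolment is remote.** Largely true. It needs a post-COVID patient who also has non-metastatic CIPN, and the same staff screen charts for both cohorts. A reader might infer that the count of 60 separate patients is in danger, but the plan's wording implies distinct people. The case for a written bar is that it costs almost nothing.

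**The bias can be stated in points, always in favour of TENS.** A reader might attempt this, but both inputs would be invented. The sign is not fixed either: recognition would favour TENS, whereas a sham patient using a personal active unit would work against it. The Quell usage log is there for compliance, and nothing says it would detect such a unit.

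**It is a pilot with a convenience sample.** True, and this limits the weight of the point. Aim 2 is nevertheless proof-of-concept effectiveness against sham.

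**Conclusion.** The omission is certain on the text, and its consequence is possible but unmeasured. As written, the plan can admit patients who already know the one feature distinguishing sham from active, in its only blinded comparison of largely patient-reported outcomes. The size is unknown and probably modest, because it depends on a rate of previous Quell use that the documents do not give.

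This is a cheap improvement to eligibility. It does not show that blinding will fail or that the result will be exaggerated by any particular amount. The conclusion assumes only that a former Quell user remembers roughly how long a session lasted.

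**What to change.** - Add to both exclusion lists: previous use of a Quell device, and previous or current participation in the other sub-study.
- Ask about both at screening, in neutral wording that does not draw attention to session length.
- Record any other previous or concurrent TENS use at baseline and at 4W, without restricting it. Specify a sensitivity analysis that omits those patients or adjusts for the recorded use. G2 already allows prognostic covariates, so previous use fits there. Concurrent use arises after randomisation, so an analysis based on it should be labelled as exploratory.
- Reconcile the description of the sham as non-functional (Section D and F2) with the 6 minutes of stimulation it delivers.

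The cost is two screening questions, one extra item at baseline and 4W, a few lines of protocol text and a few lost candidates. The acceptability sample becomes slightly narrower, because experienced users are left out. The risk of unblinding is reduced, not removed.

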Study #2: Chemotherapy and other cancer treatments can cause damage to the peripheral nerves mainly reflected in severe pain in the upper and/or lower extremities. Additional to pain, cancer treatment may cause loss of balance which affects motor capacity and is a major cause of poor quality of life. There are only minimally effective treatments for CIPN despite over 20 years of research. Few recent studies including ours have suggested that exercise intervention could be effective to restore numbness and motor capacity loss because of CIPN. Unfortunately, conventional rehabilitation programs however suffer from poor adherence and those programs for supervised settings have limitation of access for those who live in the remote areas (e.g., rural area), or could be too frail to travel after chemotherapy. This raised a significant disparity for delivering an effective therapy for those who are living in remote areas or those who are too frail to travel. Therefore, we believe the user-friendly design, and wireless practicality of Quell® is a suitable option for our CIPN population at BCM.

Our institution's Duncan Cancer Center (McNair Campus, BCM St Luke's, Houston, TX, USA) supervised by specialists in clinical and surgical oncology, has a high volume of patients that present with CIPN. Therefore, we believe our institution is a suitable place to perform this sub-study. The premise of this sub-study is that daily basis of TENS therapy could be effective to reduce pain, reduce numbness and improve both motor-capacity and mobility performance leading to improve quality of life in those who suffer from CIPN and have limited access to health care.

Section D: Purpose and Objectives

The purpose of the pilot study is to examine acceptability and proof of concept effectiveness of a wireless TENS technology to address NP due to different etiologies. Sample size (n=60) is convenient and designed to explore acceptability and feasibility.

Study #1: PASC associated FM. Eligible participants (N=30) will be screened at the BCM Post-COVID-19 Clinic for inclusion criteria.

Study #2: Patients with CIPN (N=30). Eligibility will be screened at the Duncan Cancer Center at BCM.

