Participants, who satisfy the inclusion and exclusion criteria and sign the informed consent form will be randomly assigned with ratio of 1:1 into two groups. One group will utilize TENS functional devices (Active group, AG); the other group will utilize TENS non-functional devices (Placebo group, PG). The baseline measurements will be performed, and the patients will take the programmed device home for a duration of 4 weeks. Then, the patients will come back after four weeks (4W). At this 4th week visit, both groups will be unblinded and the AG will keep their functional device and the PG group will receive a functional device. Both groups will continue to deliver 3-5 hour of stimulation daily, until their final 8th week follow up visit (8W). The primary outcomes will be pain symptoms, sleep and fatigue. Secondary outcomes include limb strength and perfusion, gait assessment (gait speed, stride length, double stance, and gait steadiness), balance, pulse oximetry, and quality of life. The coordinator will utilize a weekly spreadsheet showing utilization (therapy sessions/day, logged in the Quell health Cloud) so compliance can be monitored and those that are not using the device can be encouraged.

Section E: Protocol Risks/Subjects

E1. Risk Category

Category 1: Research not involving greater than minimum risk.

E2. Subjects

Gender:
Both

Age:
Adult (18-64 yrs), Geriatric (65+ yrs)

Ethnicity:
All Ethnicities

Primary Language:
English

Groups to be recruited will include:
Patients

Which if any of the following vulnerable populations will be recruited as subjects?

Vulnerable populations require special protections. How will you obtain informed consent, protect subject confidentiality, and prevent undue coercion?

E3. Pregnant woman/fetus

Will pregnant women and/or fetuses (as described in 45 CFR 46 Subpart B) be enrolled in the research?
No

E4. Neonates

Will neonates of uncertain viability or nonviable neonates (as described in 45 CFR 46 Subpart B) be enrolled in the research?
No

E5. Children

Will children be enrolled in the research?
No

Section F: Design/Procedure

F1. Design

Select one category that most adequately describes your research:
c) Pilot

Discuss the research design including but not limited to such issues as: probability of group assignment, potential for subject to be randomized to placebo group, use of control subjects, etc.

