Physical Activity and Health Monitoring: The subject will be given a wearable device (PAMSys) and/or a smart watch (Vivosmart 4) that will be measuring several parameters including number of steps taken, duration of sitting, standing, walking and lying, time taken and number of transitions from sit to stand, and walking speed for a minimum of 48 hours. At the end of the specific visit, the subject will be given the device, if they are given PAMSys it will be attached to pendant to wear around the neck, otherwise they may wear the smart device on their wrist. Investigators will ask the subject to return the wearable device at study completion. Subjects will either return the device at their next research visit or be given a prepaid package to mail the device back.

Optional Questionnaires at each study visit: pain, weakness, sleep, quality of life, frailty, depression, life and space, beck anxiety scale, Katz-daily living, fatigue, and user acceptability.

The supervision of this study will be by pulmonary care specialists (Study #1), and cancer care specialists (study #2) and the location will be at Baylor College of Medicine McNair Campus.

Section G: Sample Size/Data Analysis

G1. Sample Size

How many subjects (or specimens, or charts) will be used in this study?

Local: 60 Worldwide: 60

Please indicate why you chose the sample size proposed:

Convenient and selected based on available resources to demonstrate feasibility and the proof of concept effectiveness of TENS therapy for patients with NP. We plan to recruit 60 eligible subjects.

Study #1: 30 subjects Study #2: 30 subjects

G2. Data Analysis

Provide a description of your plan for data analysis. State the types of comparisons you plan (e.g. comparison of means, comparison of proportions, regressions, analysis of variance). Which is the PRIMARY comparison/analysis? How will the analyses proposed relate to the primary purposes of your study?

Independent t-test, U-test, or Chi-square (depends on type of variables) to compare between groups (AG, and PG for key baseline descriptors including demographics and relevant clinical characteristics. Those descriptors which show statistical

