significant difference, baseline value of the outcomes measured in the model, and other variables that are deemed to be prognostic, will be considered as covariates for adjusting the results in the following assessments. Appropriate mixed models (linear for continuous or Generalized Estimating Equations (GEEs) for non-continuous or non-parametric variables) will be used to test the intervention effect for each of the primary or secondary outcomes. Results will be adjusted by covariates as described above.

Section H: Potential Risks/Discomforts

H1. Potential Risks/Discomforts

Describe and assess any potential risks/discomforts; (physical, psychological, social, legal, or other) and assess the likelihood and seriousness of such risks:

The risk to participants of this study is considered to be minimal in a controlled environment with an attendant present. This research routine will not place subjects at higher risk than normal activities of daily living, and no more risk of harm or discomfort is associated with these tests than the discomfort normally incurred while performing normal muscle stretching. Subjects will be allowed rest time between trials as needed. The EMG device will detect level of fatigue and based on that we will determine the length of the sessions.

The devices and technologies are completely non-invasive, safe, non-toxic and non-ionizing. The potential risks to subject are minimal. However, like any battery powered systems, there is a minimum risk of sensor malfunctioning. In addition, the study devices are not waterproof, and although they use a low powered battery (similar to a cellphone battery), in order to avoid any risk of shock the monitor should not be submerged or saturated with fluids during operations or cleaning. It does not emit any radiation to the human body, and does not offer any significant risk to the subject.

Subjects may experience mild discomfort from the band or hydrogel pads on their legs. We will inform the subject to please notify the investigators if the band or hydrogel pads are uncomfortable.

All information we will collect about the subject will be stored in a secure location and coded in a way to maintain confidentiality. Only study personnel will have access to their records. Data collected during the study may be published and made publicly available. Data may also be shared with other research groups. However, data that could in any way identify them will not be made public or shared.

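### Section G2 chooses covariates partly by testing baseline differences between randomised arms; a short named list would serve better

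*Combined protocol and SAP*

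**What the plan says.** Section G2 (Data Analysis) plans an "Independent t-test, U-test, or Chi-square (depends on type of variables) to compare between groups" on a set of demographic and clinical variables recorded at baseline. The variables carried forward to the outcome models are those for which these tests find a "significant difference, baseline value of the outcomes measured in the model, and other variables that are deemed to be prognostic, will be considered as covariates". Covariates can therefore enter by three routes: a significant baseline difference between arms, the baseline value of the outcome, and variables judged prognostic. The plan lists neither the descriptors nor the prognostic variables, and gives no significance level for the baseline tests. Mixed models or GEEs then test the intervention effect on every primary and secondary outcome, and "Results will be adjusted by covariates as described above".

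On allocation, Section D says participants "will be randomly assigned with ratio of 1:1 into two groups", and Section F1 adds: "Randomization will be done through a computer-generated list followed by sequential allocation". Sections F1 and F2 give 15 per arm in each sub-study. No other section fixes the covariate set.

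**The concern.** The second route is sound and the third is reasonable in principle. The first selects on the wrong property. Under sound randomisation, with descriptors recorded before any stimulation, a significant difference between arms is a chance event. A covariate helps when it predicts the outcome, and a p-value for imbalance says nothing about that.

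Two consequences follow. Variables that pass the test are by construction correlated with treatment, so an irrelevant one costs more precision than an arbitrary irrelevant covariate would. And a prognostic variable with a moderate imbalance is passed over. The third route might rescue it, but because that route names nothing, the plan does not show that it would.

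What is at stake is the precision of the treatment estimates for the primary outcomes, and whether the analysis is fixed in advance. It matters because Section F2 states "Aim 2 (proof of concept effectiveness): To examine effectiveness of TENS for NP" and G2 holds the model that tests it.

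**Working it through.** The plan has no power, effect size or SD to reproduce, so what follows is illustration.

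**Inputs from the plan.** 1:1 randomisation (Sections D, F1); 15 per arm per sub-study, or 30 per arm if the two are pooled.

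**Assumptions not in the plan.** Baseline tests two-sided at 5%; K = 5, 10 or 20 descriptors, independent unless stated; treatment effect 0.8 SD; baseline-outcome correlation 0.5.

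**1. Chance that at least one descriptor is selected**, 1 − 0.95^K:
- K = 5: 1 − 0.95^5 = 22.6%
- K = 10: 1 − 0.95^10 = 40.1%
- K = 20: 1 − 0.95^20 = 64.2%

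**2. Imbalance needed for selection** (t-test), t × √(2/n):
- 15 per arm: 2.048 × √(2/15) = 0.748 SD
- 30 per arm: 2.002 × √(2/30) = 0.517 SD

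A continuous prognostic variable with a smaller imbalance is missed by this route.

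**3. Why a selected irrelevant variable is costly.** A descriptor just at the threshold has squared correlation with treatment t²/(t² + df) = 2.048²/(2.048² + 28) = 4.194/32.194 = 0.130. The standard error of the treatment effect is then multiplied by about √(1/(1 − 0.130)) = 1.07. That is the least a selected descriptor costs on average; larger imbalances and multiple selections cost more.

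**4. Simulated power, descriptors unrelated to outcome.** ANCOVA, 20,000 runs per cell (Monte Carlo error about 0.3 points). The fixed set is the baseline outcome plus one named prognostic variable with r = 0.4; the rule adds any significant descriptor.

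| K | 15/arm, fixed | 15/arm, rule | CI wider when one is selected | 30/arm, fixed | 30/arm, rule |
|---|---|---|---|---|---|
| 5 | 75.5% | 73.1% | 12% | 97.1% | 96.7% |
| 10 | 75.4% | 71.0% | 14% | 97.4% | 96.6% |
| 20 | 75.3% | 67.0% | 17% | 97.2% | 96.0% |

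The losses are 2.4, 4.4 and 8.3 points at 15 per arm, and 0.4, 0.8 and 1.2 at 30 per arm.

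**5. Two useful descriptors among the K.** Two have r = 0.3 with the outcome and the rest are unrelated. Only the baseline outcome is fixed; 15 per arm.

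| K | Baseline outcome only | Rule | Both predictors named |
|---|---|---|---|
| 5 | 67.1% | 65.4% | 74.9% |
| 10 | 66.8% | 63.5% | 74.7% |
| 20 | 67.0% | 59.6% | 75.2% |

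The rule finds at least one of the two predictors in about 10% of runs. It takes in an irrelevant descriptor in 15%, 34% or 60%.

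**6. Every descriptor predictive.** With K = 5, all at r = 0.2, on top of the fixed set in step 4, power is 75.7% (fixed) and 74.8% (rule), and the root mean squared error falls slightly, from 0.289 to 0.286. With all five at r = 0.3 the rule gains: 75.2% to 76.4%, error 0.289 to 0.270. So the rule need not do harm. Naming two of the r = 0.2 descriptors in advance gives 78.1%.

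**7. Type I error under the rule.** 4.8% to 5.1% with unrelated descriptors and 3.4% to 4.3% with predictive ones. There is no inflation when the rule is applied mechanically.

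**The case against.** The strongest reply is proportion. This is a pilot: "Sample size (n=60) is convenient and designed to explore acceptability and feasibility". It has no power target and the rule does not inflate type I error. If the descriptors are few, the loss is about 2 points at 15 per arm and under half a point if pooled. That stands, and it limits the point to an improvement.

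The remedy also has a price. Naming variables that turn out not to predict costs power at 15 per arm. With the baseline outcome otherwise alone, one such variable takes 66.9% to 65.1% and two take it to 63.6%; with the r = 0.4 variable already included, two take 75.5% to 71.9%. Two poor choices thus lose more than the rule does with five unrelated descriptors. This stands, and is why the list must be short.

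Some of the illustration is generous. Descriptors are rarely independent: with pairwise correlation 0.5, selection falls to 19%, 29% and 44%, and the power loss to about 1.9, 3.4 and 4.8 points (8,000 runs per cell). The case with five predictors at r = 0.3 implies an explained variance of 0.25 + 0.16 + 5 × 0.09 = 0.86, which is implausibly high, so no weight should rest on it. The thresholds in step 2 assume a 5% t-test, whereas G2 also allows U and Chi-square tests. The simulations use ANCOVA for a single outcome, not the planned mixed models or GEEs.

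Finally, G2 says the variables will be considered, which leaves discretion. That does not help: G2 goes on to say results will be adjusted, and discretion would remove the mechanical application on which step 7 relies.

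**Conclusion.** The concern holds. G2 states an actual rule that selects on chance imbalance instead of prognostic value, and nothing elsewhere in the plan fixes the covariates. At 15 per arm with unrelated descriptors, the cost is about 2 points of power for a short list and up to about 8 for twenty independent descriptors, or about 5 if those are correlated at 0.5. Pooling reduces it to about 1 point or less. If the descriptors do predict the outcome, the loss shrinks or vanishes, but naming good predictors in advance does better. All these figures rest on the assumptions listed above. The treatment test remains valid under mechanical use. The change is worth making because it is cheap and because G2 carries the effectiveness aim.

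**What to change.** In G2, delete the baseline significance tests as a means of choosing covariates and present baseline characteristics descriptively. State that each outcome model adjusts for the baseline value of that outcome and for one or two prognostic variables, named in the SAP before the first participant is unblinded at week 4, with sub-study added if the cohorts are pooled. If unblinding has already begun, fix and date the list before any outcome is compared by arm, and say so. Report adjustment for observed imbalances only as a sensitivity analysis.

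The cost is SAP wording. A chance imbalance in an unnamed variable would then be addressed only in the sensitivity analysis. Because poorly chosen covariates also lose power at this sample size, the list should be short and chosen for expected prognostic value.
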